Cover letter

Study protocol

ORIGINAL TITEL:

Comparison between the caudal block and other methods of postoperative pain relief in children undergoing circumcision: A prospective randomized study

Institution review board number (IRB number: 70130623).

Approval date 13\06\2023

The study conforms to the provisions of the Declaration of Helsinki in 1995 (as revised in Edinburgh 2000) and it was ethically approved by the Research Committee for Government Hospitals, Salmaniya Medical Complex, Kingdom of Bahrain (IRB number: 70130623).

Selecting the best analgesia method in pediatrics is so important. This is a randomized a prospective study conducted on 90 children who underwent circumcision. The results showed that circumcision in pediatrics using a caudal block can provide longer analgesia for the patient.

ABSTRACT

Background:

Caudal block (CB), dorsal nerve penile block (DPNB), and systemic opioids are common techniques used in pediatric surgeries to provide analgesia for penile surgery such as circumcision.

Aims: This study aimed to compare the effectiveness of the CB with other methods of postoperative pain release.

Material and Methods: The main operation pediatric theater and post-anesthesia recovery unit (PACU) in the Government Hospitals, Salmaniya Medical Complex, Bahrain.

Study subjects: Successive children aged 3 months to 3 years who had American Society of Anesthesiologists with Physical Status classification one and who had undergone elective circumcision

surgery were recruited., Children were randomized to one of three modalities of intraoperative analgesia: CB, or DPNB. And systemic opioids.

study design: Prospective, Observation-randomized, case-controlled trial study. a study Sample size: all patients, for a total of 90 boys going for circumcision surgery. I was recruited over the course of four months, starting in May 2023. The patients will be divided into three groups: A (CB), B systemic opioids, and C (DPsNB). All patients had operations and were observed, and the three groups were compared based on hemodynamic stability, pain scores, duration of sedation,

analgesia need, and parental satisfaction. where the Face, Leg, Activity, and Cry Consolability s(FLACC) pain scale and behaviors were used to observe and compare the three Groups.

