COVER LETTER

Statistical Analysis Plan

ORIGINAL TITEL:

Comparison between the caudal block and other methods of postoperative pain relief in children undergoing circumcision: A prospective randomized study

This study was approved by the research ethics committee operates Institution Review Board number 70130623

The study conforms to the provisions of the Declaration of Helsinki in 1995 (as revised in Edinburgh 2000) and it was ethically approved by the Research Committee for Government Hospitals, Salmaniya Medical Complex, Kingdom of Bahrain (IRB number: 70130623).

Data management

The collected data were recorded then presented and statistically analyzed by computer using SPSS 27.0 for Windows (*SPSS Inc., Chicago, IL, USA*) and Prism Graphpad version 9.4.1 (*Graphpad, San Diego, USA*). A test of normality was done using the Kolmogorov-Smirnov test. Kruskal-Wallis test was used to compare between groups for numerical variables, while Chi-square and Fisher's Exact test were used for categorical variables. Linear regression analysis was used to detect the predictors of pain scale. All tests were two-sided. The accepted level of significance in this work was ($p \leq 0.05$). A p -value ≤ 0.01 was considered highly statistically significant and $p > 0.05$ was considered non-statistically significant.

Results

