A total of 90 patients had participated in this current study. The study subjects were classified into 3 main groups. The first group (group A) received general anesthesia with caudal block including 29 patients. The second group (Group B) represented general anesthesia with an opioid group with a total of 33 participants, while the last group (Group C) was patients with a penile block 28 patients. Group B was significantly older in comparison with the other two groups, while Group A was the youngest age group as described in Table 1. No significant difference had been observed regarding operation duration among the three groups. Sevo Mac consumption is significantly lower in group A in comparison with the other two groups. Fentanyl consumption intra and post-operative is higher in group B followed by group C, while the lowest level of consumption with among group A patients. Participants' heart rates are shown in Figure 1. Group C significantly showed a higher mean heart rate intraoperative, 5, 10, 20, 30, and 60 minutes postoperative, while group B showed the lowest mean heart rate in the three groups ($p < 0.005$). The behavioral score is represented in figure 2 which had been measured 5, 10, 20, 30, and 60 minutes postoperative. Group C significantly demonstrated a higher percentage of severe discomfort in comparison with the other two groups in 5, 10, 20, and 30 minutes post-operative (82.1, 25.0%, 21.4%, and 3.6% respectively). The percentage of severe discomfort in group B in 5, 10, 20, and 30 minutes post-operative was 18.2, 6.1%, 3.0%, and 0.0% respectively, while only one patient expressed severe discomfort in 5, 10, and 20 minutes in group A. The pain scale was much higher among group C, while group A showed the lowest mean pain scale (Figure 3).

Table 2 represents the crying scale (5, 10, 20, 30, 60 minutes postoperative) among the studied groups. Group C showed a higher percentage of crying in comparison with the other two groups, however, the relation was non-significant.

The movement scale also was significantly different between the 3 groups in 5, 20, and 30 minutes post-operative (Table 3). Similarly, a significant difference was shown between the 3 groups in the agitation scale in 5, 10, and 30 minutes postoperative (Table 4). Table 5, demonstrated a

statistically significant difference between the 3 groups on the posture scale in 5, and 30 minutes post-operative.

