30 minutes postoperative				
Not crying	13 (44.8)	15 (45.5)	14 (50.0)	0.912
Crying but responds to tender Loving care	16 (55.2)	18 (54.5)	14 (50.0)	

60 minutes postoperative

[figure not shown]
Not crying	17 (58.6)	19 (57.6)	12 (42.9)	0.407
Crying but responds to tender Loving care	12 (41.4)	14 (42.4)	16 (57.1)	

The comparison between groups was done using Chi square test (χ^2)

[figure not shown]
5 Minutes

10 Minutes

[figure not shown]

20 Minutes

[figure not shown]

- Relaxed and comfortable
- Mild discomfort
- Moderate pain
- Severe discomfort/pain

30 Minutes

60 Minutes

Behavioral score among studied groups. *Fisher's exact test was used* FLACC scores from 0-10 , zero is analgesia, 1-3 is for mild pain, 4-6 is for moderate pain, and 7-10 is for severe pain

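### The SAP says Group C had significantly more severe discomfort than both other groups at four times; the exact test supports this only at 5 minutes, and neither document says who scored or whether the arm was concealed

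*Protocol*

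**What the plan says.** The Protocol abstract (study design) states that "All patients had operations and were observed, and the three groups were compared based on hemodynamic stability, pain scores", with FLACC and behaviours as the observed measures. It does not say who scored, where that person was during surgery, or whether the arm was hidden from them. The SAP is equally silent.

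The SAP's Data management section sets the significance level at 0.05, says that "All tests were two-sided", and that "Chi-square and Fisher's Exact test were used for categorical variables". For the behavioural score the figure legend says "Fisher's exact test was used". It lists four categories, and its FLACC key places the top band at "7-10 is for severe pain".

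The SAP's Results section states that "Group C significantly demonstrated a higher percentage of severe discomfort in comparison with the other two groups" at 5, 10, 20 and 30 minutes, and prints percentages for Groups B and C and a count for Group A. It prints no p-value for this comparison.

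**The concern.** The Results sentence makes two claims at each of four times: that the severe category differs by arm, and that Group C exceeds both other groups. At 10 and 20 minutes only 10 and 8 children of 90 are severe, and at 30 minutes only one, so it is not obvious that a two-sided exact test supports both claims at each time. If it does not, readers are told that the disadvantage of the penile block group persists, as a severe-pain finding, beyond the time for which the data show it.

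The outcome is also an observer's judgement. With so few events, one child's rating can matter. With no description of the scorer or of concealment, a reader cannot tell whether the ratings could have been shaped by knowledge of the arm.

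**Working it through.** **Inputs.** Group sizes: A 29 ("general anesthesia with caudal block including 29 patients"), B 33, C 28, from SAP Results. Severe percentages, same section: C 82.1, 25.0, 21.4, 3.6; B 18.2, 6.1, 3.0, 0.0. Group A is described as having one severe patient at 5, 10 and 20 minutes. I read this as one at each time, and take zero at 30 minutes, where none is mentioned.

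**Counts.** 23/28 = 82.1%, 7/28 = 25.0%, 6/28 = 21.4%, 1/28 = 3.6%; 6/33 = 18.2%, 2/33 = 6.1%, 1/33 = 3.0%, 0/33 = 0.0%. All are whole children.

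**Calibration.** The SAP gives no p-value here to reproduce. As a check on the denominators, Pearson chi-square on the crying counts returns all five p-values of Table 2 (0.344, 0.375, 0.200, 0.912, 0.407).

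**Three-arm exact test (Fisher-Freeman-Halton), severe v not severe.** With T severe children in all, P(a,b,c) = C(29,a)·C(33,b)·C(28,c) / C(90,T). The p-value sums P over all tables no more probable than the observed one. At 30 minutes T = 1 and the three possible tables have probabilities 29/90, 33/90 and 28/90; the observed one is the smallest, so p = 28/90 = 0.31.

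| Minutes | Severe A/B/C | Three-arm p | C v A | C v B |
|---|---|---|---|---|
| 5 | 1/6/23 | <0.0001 | <0.0001 | <0.0001 |
| 10 | 1/2/7 | 0.030 | 0.025 | **0.067** |
| 20 | 1/1/6 | 0.025 | **0.052** | 0.041 |
| 30 | 0/0/1 | 0.31 | 0.49 | 0.46 |

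**The two decisive pairwise values.**
- 10 minutes, C v B: 9 severe among 61. P(k severe in C) = C(28,k)·C(33,9−k)/C(61,9). Tables as improbable as k = 7: k = 7, 8, 9, 1, 0, giving 0.0361 + 0.0059 + 0.0004 + 0.0224 + 0.0022 = 0.067.
- 20 minutes, C v A: 7 severe among 57. P(k) = C(28,k)·C(29,7−k)/C(57,7). Tables as improbable as k = 6: k = 6, 7, 0, giving 0.0413 + 0.0045 + 0.0059 = 0.052.

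These are unadjusted for multiple comparisons.

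**One child re-rated, three-arm p.**

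| Change | 10 min, exact | 10 min, Pearson | 20 min, exact | 20 min, Pearson |
|---|---|---|---|---|
| None | 0.030 | 0.018 | 0.025 | 0.019 |
| One fewer severe in C | 0.090 | 0.049 | 0.088 | 0.056 |
| One more severe in A | 0.064 | 0.045 | 0.074 | 0.046 |
| One more severe in B | 0.052 | 0.036 | 0.090 | 0.049 |

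**The same question at 5 minutes.** With A and B fixed, C v B stays below 0.05 until C falls from 23 to 11 (12/28 gives 0.0496, 11/28 gives 0.089). C v A and the three-arm test hold until C falls to 6.

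**The case against.** *The sponsor may have tested all four categories.* This stands as a limit. The legend does not say that severe was collapsed against the rest, and a reader should not infer that scores were cut at 7 and then tested. The four-category counts are in a figure not shown, so that test cannot be checked. But the Results sentence is worded as a difference in the percentage with severe discomfort, and severe versus not severe is the table that tests that wording.

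*The result depends on the test.* It does. Uncorrected Pearson chi-square would put both failing pairs below 0.05: C v B at 10 minutes is 61·(7·31 − 21·2)²/(28·33·9·52) = 4.32, p = 0.038; C v A at 20 minutes is 57·(6·28 − 22·1)²/(28·29·7·50) = 4.28, p = 0.039. Pooling A and B gives 0.009 and 0.010, and at most 0.031 after one re-rating. However, expected severe counts in these tables are below 5 (2.5 to 3.7 per arm in the three-arm tables; 4.1 and 4.9, and 3.4 and 3.6, in the two pairs). The SAP names Fisher's test for this outcome, and a pooled comparison is not the stated one. Pearson does not rescue 30 minutes (0.33).

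*Single-child fragility suggests biased scoring.* A reader might infer this; it does not follow. A p-value near 0.03 with 8 to 10 events will usually move past 0.05 when one event changes, whoever scored. Nor do the documents show that scorers knew the arm: blinding is not described, which is a different statement. Individual scores are not given, so whether any child sat near the cut is unknown.

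*The 5-minute result is then safe.* It withstands many isolated rating errors, but that is not protection against a systematic shift in one arm.

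**Conclusion.** The SAP's statement that Group C had significantly more severe discomfort than both other groups is supported on the severe category only at 5 minutes. At 10 and 20 minutes there is a three-arm difference (0.030 and 0.025), but one of the two claimed pairwise differences narrowly misses 0.05 in each case (0.067 and 0.052). At 30 minutes there is one severe child and no evidence of a difference (0.31). The 10- and 20-minute three-arm results are also within one child of 0.05 under the exact test, and less so under Pearson.

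This rests on counts recovered from the printed percentages, on one severe child in Group A at each of 5, 10 and 20 minutes and none at 30, and on the exact test applied to severe versus not severe.

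Separately, the scorer and any concealment of the arm are undescribed for every observer-rated outcome. The documents do not allow the direction or size of any resulting bias to be estimated, and narrowing the claim to 5 minutes does not remove that uncertainty.

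**What to change.** 1. In SAP Results, restrict the statement that Group C significantly exceeded both other groups on severe discomfort to 5 minutes.
2. At each time report the counts, the three-arm exact p-value and the pairwise exact p-values. Add a short table showing the effect of re-rating one child at 10 and 20 minutes.
3. State whether the behavioural score was tested in two or four categories. If four, give those counts and do not word the result as a difference in severe discomfort.
4. State who scored the 90 children and whether they knew the arm. If they did, qualify all observer-rated results, including those at 5 minutes.
5. For any further enrolment, add a protocol sentence that scoring is done by existing recovery staff who were not in theatre and are not told the arm, without withholding treatment information needed for care.

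Cost: a small reanalysis of data already held, a few sentences of text, and a narrower claim. Whether item 5 needs extra staff cannot be judged, because the documents do not describe recovery staffing.

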COVER LETTER

Statistical Analysis Plan

ORIGINAL TITEL:

Comparison between the caudal block and other methods of postoperative pain relief in children undergoing circumcision: A prospective randomized study

This study was approved by the research ethics committee operates Institution Review Board number 70130623

The study conforms to the provisions of the Declaration of Helsinki in 1995 (as revised in Edinburgh 2000) and it was ethically approved by the Research Committee for Government Hospitals, Salmaniya Medical Complex, Kingdom of Bahrain (IRB number: 70130623).

Data management

The collected data were recorded then presented and statistically analyzed by computer using SPSS 27.0 for Windows (*SPSS Inc., Chicago, IL, USA*) and Prism Graphpad version 9.4.1 (*Graphpad, San Diego, USA*). A test of normality was done using the Kolmogorov-Smirnov test. Kruskal-Wallis test was used to compare between groups for numerical variables, while Chi-square and Fisher's Exact test were used for categorical variables. Linear regression analysis was used to detect the predictors of pain scale. All tests were two-sided. The accepted level of significance in this work was ($p \leq 0.05$). A p -value ≤ 0.01 was considered highly statistically significant and $p > 0.05$ was considered non-statistically significant.

Results

A total of 90 patients had participated in this current study. The study subjects were classified into 3 main groups. The first group (group A) received general anesthesia with caudal block including 29 patients. The second group (Group B) represented general anesthesia with an opioid group with a total of 33 participants, while the last group (Group C) was patients with a penile block 28 patients. Group B was significantly older in comparison with the other two groups, while Group A was the youngest age group as described in Table 1. No significant difference had been observed regarding operation duration among the three groups. Sevo Mac consumption is significantly lower in group A in comparison with the other two groups. Fentanyl consumption intra and post-operative is higher in group B followed by group C, while the lowest level of consumption with among group A patients. Participants' heart rates are shown in Figure 1. Group C significantly showed a higher mean heart rate intraoperative, 5, 10, 20, 30, and 60 minutes postoperative, while group B showed the lowest mean heart rate in the three groups ($p < 0.005$). The behavioral score is represented in figure 2 which had been measured 5, 10, 20, 30, and 60 minutes postoperative. Group C significantly demonstrated a higher percentage of severe discomfort in comparison with the other two groups in 5, 10, 20, and 30 minutes post-operative (82.1, 25.0%, 21.4%, and 3.6% respectively). The percentage of severe discomfort in group B in 5, 10, 20, and 30 minutes post-operative was 18.2, 6.1%, 3.0%, and 0.0% respectively, while only one patient expressed severe discomfort in 5, 10, and 20 minutes in group A. The pain scale was much higher among group C, while group A showed the lowest mean pain scale (Figure 3).

Table 2 represents the crying scale (5, 10, 20, 30, 60 minutes postoperative) among the studied groups. Group C showed a higher percentage of crying in comparison with the other two groups, however, the relation was non-significant.

The movement scale also was significantly different between the 3 groups in 5, 20, and 30 minutes post-operative (Table 3). Similarly, a significant difference was shown between the 3 groups in the agitation scale in 5, 10, and 30 minutes postoperative (Table 4). Table 5, demonstrated a

statistically significant difference between the 3 groups on the posture scale in 5, and 30 minutes post-operative.

Table 6 explains that the type of block, fentanyl intraoperative and postoperative was the predictor of the 5-minute pain scale, while the type of block was only the significant predictor of the 10, 20, and 30-minute pain scale. The type of block and weight of participants were the predictors of the pain scale 60 minutes postoperative

Comparison between the caudal block and other methods of postoperative pain relief in children undergoing circumcision: A prospective randomized study

This study was approved by the research ethics committee operates Institution Review Board number 70130623

Table 1. Demographic data of children who underwent circumcision

Demographic data of children who underwent circumcision Variables	Group A (n=29) Mean±SD	Group B (n=33) Mean±SD	Group C (n=28) Mean±SD	P-value*	Significant pairs**
Age (months)	16.0±7.5	41.8±43.3	16.3±19.7	0.002	Group A vs.s Group B AND Group B vs Group C
Weight (KG)	10.3±2.4	11.3±3.8	9.0±5.1		0.130
Operation duration (minutes)	14.6±3.5	15.1±4.6	16.3±6.1		0.523
Sevo mac	0.5±0.3	2.0±1.6	1.5±0.2	<0.001	Group A vs. Group B AND Group A vs. Group C
Fentanyl intraoperative	9.9±5.4	22.1±9.1	16.4±5.4	<0.001	Group A vs Group B Group A vs. Group C AND Group B vs. Group C
Fentanyl postoperative	4.8±3.1	10.5±4.6	5.2±2.5	<0.001	Group A vs. Group B AND Group B vs. Group C

Comparison between the caudal block and other methods of postoperative pain relief in children undergoing circumcision: A prospective randomized study

This study was approved by the research ethics committee operates Institution Review Board number 70130623

Table 2:

represents the crying scale (5, 10, 20, 30, 60 minutes postoperative) among the studied groups. Group C showed a higher percentage of crying in comparison with the other two groups, however, the relation was non-significant

Crying scale (5, 10, 20, 30, 60 minutes postoperative) among studied groups

Brief title: Participants' Crying Scale

[figure not shown]
Variables	Group A (n=29) N (%)	Group B (n=33) N (%)	Group C (n=28) N (%)	P -value
5 minutes postoperative				
Not crying	19 (65.5)	19 (57.6)	13 (46.4)	0.344
Crying but responds to tender Loving care	10 (34.5)	14 (42.4)	15 (53.6)	
10 minutes postoperative				
Not crying	15 (51.7)	17 (51.5)	10 (35.7)	0.375
Crying but responds to tender Loving care	14 (48.3)	16 (48.5)	18 (64.3)	
20 minutes postoperative				
Not crying	19 (65.5)	16 (48.5)	12 (42.9)	0.200
Crying but responds to tender Loving care	10 (34.5)	17 (51.5)	16 (57.1)	
30 minutes postoperative				
Not crying	13 (44.8)	15 (45.5)	14 (50.0)	0.912
Crying but responds to tender Loving care	16 (55.2)	18 (54.5)	14 (50.0)	

60 minutes postoperative

[figure not shown]
Not crying	17 (58.6)	19 (57.6)	12 (42.9)	0.407
Crying but responds to tender Loving care	12 (41.4)	14 (42.4)	16 (57.1)	

The comparison between groups was done using Chi square test (χ^2)

[figure not shown]
5 Minutes

10 Minutes

[figure not shown]

20 Minutes

[figure not shown]

- Relaxed and comfortable
- Mild discomfort
- Moderate pain
- Severe discomfort/pain

30 Minutes

60 Minutes

Behavioral score among studied groups. *Fisher's exact test was used* FLACC scores from 0-10 , zero is analgesia, 1-3 is for mild pain, 4-6 is for moderate pain, and 7-10 is for severe pain

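### Heart rate appears to be compared with no age adjustment although Group B is printed as about 26 months older than A and C, and B's printed ages do not fit the eligibility range

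*SAP*

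**What the plan says.** The Protocol abstract lists haemodynamics first among its comparisons: "the three groups were compared based on hemodynamic stability, pain scores, duration of sedation". Its eligibility line reads "Successive children aged 3 months to 3 years".

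In the SAP, the Data management section gives one rule for numerical outcomes, "Kruskal-Wallis test was used to compare between groups for numerical variables", and one model, "Linear regression analysis was used to detect the predictors of pain scale". No age adjustment of heart rate is mentioned anywhere.

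The SAP Results say "Group B was significantly older in comparison with the other two groups". Table 1 prints ages in months (mean±SD) of 16.0±7.5 in A (n=29), 41.8±43.3 in B (n=33) and 16.3±19.7 in C (n=28), with p=0.002 and the pairs A–B and B–C flagged. On the outcome, "Participants' heart rates are shown in Figure 1". The text puts C highest at six times (during surgery and at 5, 10, 20, 30 and 60 minutes after it) and B lowest, with a single p<0.005 and no pairwise contrast for B.

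**The concern.** The arm with the lowest heart rate is also the arm that is older by more than two years, in a trial meant to enrol children up to 3 years of age. If heart rate falls with age in young children, an unadjusted rank test credits some or all of that age effect to the treatment. At stake is the reading of a comparison that the Protocol names.

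There is a problem that comes before this one. The printed ages conflict with the eligibility range, so an adjustment built on them is only as good as the ages themselves.

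**Working it through.** **1. The printed p-value for age.** Kruskal-Wallis needs individual data, so p=0.002 can only be bracketed from Table 1.
- Grand mean = (29×16.0 + 33×41.8 + 28×16.3)/90 = 25.55.
- Between-group sum of squares = 29×9.55² + 33×16.25² + 28×9.25² ≈ 13,755.
- Within-group sum of squares = 28×7.5² + 32×43.3² + 27×19.7² = 72,050.
- ANOVA: F = (13,755/2)/(72,050/87) = 8.30, p=0.0005. Welch ANOVA: F=5.59, p=0.007.

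The printed value lies between the two and is credible.

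**2. Age gaps** (Welch intervals, SE = √(s₁²/n₁ + s₂²/n₂)).
- B−A: 41.8−16.0 = 25.8; SE = √(56.81+1.94) = 7.67; t=2.032 on 34.2 df; 95% CI 10.2 to 41.4.
- B−C: 41.8−16.3 = 25.5; SE = √(56.81+13.86) = 8.41; t=2.013 on 46.3 df; 95% CI 8.6 to 42.4.
- C−A: 0.3; SE = 3.97; 95% CI −7.8 to 8.4.

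**3. Do the ages fit the eligibility range?** For ages between 3 and U months with mean m, the largest possible SD is √[(U−m)(m−3)n/(n−1)].

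| Arm | Printed mean, SD | Largest SD, U=36 | Largest SD, U=48 |
|---|---|---|---|
| A | 16.0, 7.5 | 16.4 | 20.8 |
| B | 41.8, 43.3 | mean is out of range | 15.75 |
| C | 16.3, 19.7 | 16.5 | 20.9 |

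A fits on both readings and B on neither. C conflicts only if 3 years ends at 36 months. With a youngest child of 3 months, the oldest child in B must be at least 41.8 + (32/33×43.3²)/(41.8−3) = 88.7 months.

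**4. What age alone could do to B's contrasts.** No heart-rate values or age slope are available, so this is illustration only. For an assumed straight-line fall of 0 to 0.5 beats/min per month, the age gap shifts B−A by 0 to 0.5×25.8 = 12.9 beats/min and B−C by 0 to 0.5×25.5 = 12.75, both downwards.

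A simulation with no treatment effect used lognormal ages matched to Table 1 and a residual SD of 15 beats/min (both assumptions). Kruskal-Wallis rejected at 0.05 in about 4% of trials at slope 0, 8% at 0.1, 26% at 0.25 and 59% at 0.5.

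**5. C versus A.** On a straight line the shift is at most 0.5×0.3 = 0.15 beats/min, but that depends on linearity. C's mean lies only 16.3−3 = 13.3 months above the lowest eligible age, less than its SD of 19.7, so C must be right-skewed. A is not forced to be (13.0 against 7.5).

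Matched lognormals (median = mean/√(1+SD²/mean²)) give medians of 14.5 months in A and 10.4 in C, with 34% and 56% under 12 months. These are rough, since the curve for C puts about 10% below 3 months. If the fall in heart rate is steepest in infancy, C would lie above A with no treatment effect, which is the reported direction.

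**6. Precision cost of adjusting for linear age.** Variance inflation = 1 + (d²/72,050)/(1/n₁+1/n₂).
- B−A: 1.143, so intervals are √1.143 = 1.069 times as wide.
- B−C: 1.137, so 1.066 times as wide.
- C−A: 1.000.

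**7. Children lost by restricting to 3–36 months.** A single older child in B would have to be 33×41.8 − 32×36 = 227.4 months old, so at least two exceed 36 months if all are under 18 years (216 months). That is only a floor. The matched lognormal puts 40% of B, about 13 of 33, above 36 months.

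**The case against.** The strongest reply is that randomization makes the unadjusted test valid on average, so adjustment is a matter of efficiency; and if randomization failed, adjusting for age does not restore a treatment effect. Both halves are sound, and the second is why allocation has to be checked. The first does not settle how to read this particular result, where the imbalance is large and sits on the arm with the extreme heart rate.

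It is also fair that the test for heart rate is inferred from the general rule, that Figure 1 may print pairwise results, and that the link between age and heart rate comes from outside the documents. The assumed slope range starts at zero. These points limit how strongly the concern can be put, but they do not remove it.

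A reader might infer more than the documents support:
- **That B's low heart rate is an age artefact.** No heart-rate values or age slope are given.
- **That C above A is safe because the mean ages match.** Step 5 shows that equal means are not enough.
- **That randomization failed.** An age p-value of 0.002 and a design line that mixes randomized with observational and case-control terms raise the question; they do not answer it.
- **That ineligible children were certainly enrolled.** A misprint in Table 1 would explain the ages equally well, and would shrink the imbalance.

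**Conclusion.** The concern holds in a limited form and should be acted on, with moderate confidence. The firm part needs no outside assumption: B's printed ages contradict the eligibility range on either reading of 3 years, and no age adjustment of heart rate is described despite gaps of 25.8 and 25.5 months.

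The conditional part is confounding. If heart rate falls with age, B's contrasts mix age with treatment. If the fall is non-linear, C versus A may be affected too. The size of the bias cannot be computed from the documents. The Protocol's statement that caudal block gives longer analgesia does not rest on heart rate.

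**What to change.** 1. Verify ages against source and reconcile them with the eligibility range, stating whether 3 years ends at 36 or 48 months. Report how many children in each arm fall outside it. Check and describe how allocation was done. If ages are corrected, recompute the imbalance before any modelling.
2. Then add a repeated-measures heart-rate model over the six time points, with treatment, time, treatment-by-time and age, allowing age to be non-linear. Give adjusted differences with 95% CIs for all three contrasts. Label it post hoc, because the imbalance has been seen, and present it as a sensitivity analysis beside Kruskal-Wallis.
3. Repeat the model in children within the eligible age range, stating the number lost per arm.
4. Until this is done, do not read heart-rate differences between arms as treatment effects.

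The cost is reanalysis only, since age is already recorded. Precision falls as in step 6 of the check, and further with a non-linear term, before any gain from variance that age explains. The restricted analysis may lose far more of B than the minimum of two.

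### The SAP does not plan caudal-versus-opioid and caudal-versus-penile contrasts with confidence intervals for pain, behaviour or crying, and its group-specific statements go beyond its three-group tests

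*SAP*

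**What the plan says.** The protocol abstract, under Aims, states: "This study aimed to compare the effectiveness of the CB with other methods of postoperative pain release". With three arms, that means A vs B and A vs C.

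The SAP, under Data management, gives the between-group methods in one sentence: "Kruskal-Wallis test was used to compare between groups for numerical variables", with chi-square and Fisher's exact tests for categorical ones. It adds "Linear regression analysis was used to detect the predictors of pain scale", two-sided testing, and a rule by which a p-value above 0.05 "was considered non-statistically significant". It names no pairwise procedure, effect measure, confidence interval or multiplicity rule.

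The SAP's Results section then makes statements about particular groups. On crying: "Group C showed a higher percentage of crying in comparison with the other two groups, however, the relation was non-significant". On severe discomfort, it describes C as significantly higher than the other two groups at 5, 10, 20 and 30 minutes. Movement, agitation and posture are described only as differing among the three groups.

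Two items go beyond omnibus testing. Table 1 has a column headed "Significant pairs" for age, sevoflurane MAC and fentanyl. The regression summary says that "the type of block was only the significant predictor of the 10, 20, and 30-minute pain scale".

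**The concern.** A small three-group p-value says that at least one group differs. It does not say which group, by how much, or whether caudal block differs from the opioid arm in particular. If the signal comes mostly from the penile-block arm, the omnibus test can be extreme while caudal versus opioid, half of the stated aim, remains open.

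The opposite error is also possible. A three-group result above 0.05 is labelled non-significant with no interval, so the reader cannot see how large a difference the data still allow.

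At stake is whether the trial's statements about individual methods rest on comparisons that were planned and made.

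**Working it through.** **1. Reproduce the SAP's own figures.** Table 2 is the only between-group comparison whose full counts are in the documents. Pearson chi-square on each 3x2 table has 2 df, so p = exp(-χ²/2). At 20 minutes, crying is 10/29, 17/33 and 16/28 (43 of 90). Expected crying counts are 13.86, 15.77 and 13.38, χ² = 3.223, and p = exp(-1.612) = 0.1995. Across 5, 10, 20, 30 and 60 minutes the recomputed p-values are 0.3445, 0.3755, 0.1995, 0.9122 and 0.4068, against the stated 0.344, 0.375, 0.200, 0.912 and 0.407. So Table 2 gives crying one omnibus p-value per time point.

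**2. Rebuild severe-discomfort counts from the Results percentages.**
- C (n=28): 82.1, 25.0, 21.4 and 3.6% give 23, 7, 6 and 1.
- B (n=33): 18.2, 6.1, 3.0 and 0.0% give 6, 2, 1 and 0.
- A (n=29): read as 1 at each of 5, 10 and 20 minutes. No case is mentioned at 30 minutes, so it is taken as 0.

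**3. Test the pairs.** Severe is taken as yes/no. Tests are two-sided Fisher, unadjusted. Differences are in percentage points with Newcombe 95% CIs.

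| Time | C-A | C-B | A-B |
|---|---|---|---|
| 5 min | +78.7 (56.3 to 89.1), p<0.001 | +64.0 (39.9 to 77.8), p<0.001 | -14.7 (-31.2 to 2.0), p=0.109 |
| 10 min | +21.6 (3.1 to 40.1), p=0.025 | +18.9 (0.6 to 37.8), p=0.067 | -2.6 (-16.5 to 11.8), p=1.0 |
| 20 min | +18.0 (0.3 to 36.3), p=0.052 | +18.4 (1.8 to 36.7), p=0.041 | +0.4 (-12.2 to 14.4), p=1.0 |
| 30 min | +3.6 (-8.5 to 17.7), p=0.49 | +3.6 (-7.3 to 17.7), p=0.46 | 0.0 (-10.4 to 11.7), p=1.0 |

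The interval method, shown for A-B at 5 minutes:
- Wilson limits are 0.0061 to 0.1718 for 1/29 = 0.0345, and 0.0861 to 0.3439 for 6/33 = 0.1818. The difference is -0.1473.
- Lower limit = -0.1473 - √[(0.0345-0.0061)² + (0.3439-0.1818)²] = -0.312.
- Upper limit = -0.1473 + √[(0.1718-0.0345)² + (0.1818-0.0861)²] = +0.020.

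**4. Compare with the omnibus test.** The three-group yes/no chi-square p-values are 1.6×10⁻¹⁰, 0.018, 0.019 and 0.33 at 5, 10, 20 and 30 minutes. At 5 minutes the omnibus result is extreme while the A-B interval includes zero, so the signal comes mainly from C.

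**5. Crying by pair.** C-A is +19.1 points (-6.3 to 41.4) at 5 minutes, +16.0 (-9.3 to 38.6) at 10, +22.7 (-3.0 to 44.5) at 20, -5.2 (-29.1 to 19.6) at 30 and +15.8 (-9.7 to 38.5) at 60. Fisher p-values run from 0.11 to 0.79. The summary that C cried more does not hold at 30 minutes: 50.0% in C, 55.2% in A and 54.5% in B.

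**6. Error rate if both contrasts are tested at 0.05.** 1 - 0.95² = 9.75%, treating them as independent. They share group A, so this is only a guide.

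**The case against.** A reader might infer that the plan produces nothing but omnibus p-values and never estimates a caudal contrast. The documents do not support that. Table 1 reports pairs for age, sevoflurane and both fentanyl variables, and analgesia need is a comparison outcome in the protocol. Welch tests on the Table 1 means and SDs agree with the flagged pairs. They also agree with the absence of an A-C flag for postoperative fentanyl (difference -0.4, 95% CI -1.9 to 1.1, p=0.59). The planned regression would give A-B and A-C differences if block were entered as two indicators with caudal as reference. Tables 3 to 6, the figures and the Table 1 pairwise footnote are not in the supplied text, so what was reported for the pain scale cannot be checked.

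The numerical examples also have limits. The 10- and 20-minute results depend on the method: for C-B at 10 minutes and C-A at 20 minutes, Fisher is above 0.05 while the Newcombe interval just excludes zero. The yes/no split is not the reported test, which used a four-level score. Pairwise testing turns no crying result significant, and Table 2 gives the counts from which a reader can work out differences.

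All of this stands, and it narrows the point. It does not supply what is missing: a single 1-2-3 code for block would not give the two contrasts, the Table 1 pairs do not cover pain, behaviour or crying, and a significant four-level omnibus test would still not support a statement about the severe category in a particular pair.

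**Conclusion.** The point holds in a limited form. For pain, behaviour and crying, the SAP does not plan the two contrasts that its aim requires, with estimates and intervals. It cannot be confirmed that the regression fills the gap.

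The severe-discomfort statement about C against both other groups is supported at 5 minutes, borderline for one pair at each of 10 and 20 minutes, and unsupported at 30 minutes, where it rests on one child. Caudal versus opioid is unresolved on this outcome. That is not evidence that the two are equivalent: at 5 minutes the interval runs from 31.2 points in favour of caudal to 2.0 points against. Nor do the crying data show a missed effect. They show intervals too wide to rule one out.

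These results assume counts rebuilt from rounded percentages, one severe case in A at each of 5, 10 and 20 minutes and none at 30, severe treated as yes/no, and no multiplicity adjustment.

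**What to change.** In Data management:
- Name A vs B and A vs C as the planned contrasts for each pain outcome.
- Report each difference with a 95% CI: Hodges-Lehmann for scores, risk difference for crying and severe discomfort.
- Control alpha across the two contrasts by Holm or closed testing, and state which. The choice can matter: at 10 minutes the A-C Fisher p of 0.0253 just misses Holm's first step of 0.025, but passes a closed test after the yes/no omnibus p of 0.018.
- Enter type of block in the regression as two indicators with caudal as reference, and report coefficients with intervals.
- Name the method behind the Table 1 pairs.
- Limit each group-specific statement in Results to what its own contrast supports.

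The cost is SAP wording and extra tabulation from existing data, with no new data collection. The downside is longer tables, and some claims will become visibly imprecise or be withdrawn.
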